3.5.4 Follow-up Period

Day 112±4 (Visit 7/Week 16) to Day 140±2 (Visit 8/Week 20)

The Follow-up Visit will occur approximately 4 weeks after the last dose of study drug. Subjects should arrive under fasted conditions (i.e., overnight fast, at least 10 hours prior to blood and urine sample collection). Please refer to [Table 1](#) for the list of follow-up procedures to be performed.

For subjects who discontinue the study prematurely after receiving at least one dose of study drug, follow-up procedures, as described for Visit 8 should be performed approximately 4 weeks after the last dose of study drug.

3.5.5 Study Restrictions

3.5.5.1 Previous and Concomitant Medication Restrictions

3.5.5.1.1 Prohibited Psoriasis Therapy and Immunomodulation Therapy

[figure not shown]
Use of the following therapies will NOT be allowed during the Prohibited Period as described in [Table 2](#).

Table 2. Psoriasis Therapy and Immunomodulation Therapy Restrictions

Prohibited Period	Medication(s)
24 weeks prior to Visit 2 till after the last study visit (Visit 8)	
• IL-12/IL-23p40 inhibitor (e.g., ustekinumab)• IL-23p19 inhibitor (e.g., guselkumab, mirikizumab, risankizumab, tildrakizumab)
12 weeks (or 5 times the PK half-life, whichever is longer) prior to Visit 2 till after the last study visit (Visit 8)	
• Biologic agents other than above (including marketed or investigational)• Investigational systemic therapies
28 days or 5 times the PK half-life (whichever is longer) prior to Visit 2 till after the last study visit (Visit 8)	
• Acitretin• Methotrexate• Cyclosporine• Apremilast• Oral/parental corticosteroids (including intramuscular or intraarticular administration)• Tofacitinib• Fumaric acid ester• Other immunomodulating systemic treatment• Psoralen plus ultraviolet A (PUVA) therapy• Ultraviolet A (UVA) therapy• Ultraviolet B (UVB) therapy• Investigational topical therapies
14 days prior to Visit 2 till after the last study visit (Visit 8)	
• Topical corticosteroids• Topical vitamin A or D analog preparations• Anthralin• Topical calcineurin inhibitors (e.g., cyclosporine)

Use of one (1) topical non-medical moisturizer (e.g., Cetaphil®) will be allowed during the study, however it will be prohibited within 12 hours prior to the study visit.

Note: If a subject develops significant clinical exacerbation of their psoriasis at any time during the entire duration of the study, study drug may be withdrawn and the subject will be treated clinically per existing standard of care.

3.5.5.1.3 Permitted Medications to be used with Caution

Permitted medications ([Appendix 1](#)) are based on nonclinical and clinical drug-drug interaction data with JTE-451. [REDACTED]

3.5.5.1.4 General Medication-related Protocol Instructions:

- Generally, changes in medication dose/route of administration or initiation of new medications during the conduct of the study is not recommended unless such actions are considered medically necessary;
- All medications taken by the subject, including over-the-counter, herbal, traditional, ayurvedic compounds (whether permitted or excluded by the protocol) must be documented in the case report form (CRF), as described in Section [3.5.6.10](#);
- Contact the Medical Monitor with questions regarding prior/concomitant therapy.

3.5.5.2 Dietary Restrictions

Grapefruit juice and grapefruit are not permitted for at least 3 days prior to Visit 2 and during the Treatment Period.

3.5.5.3 UV-Related Restrictions

Every effort should be made to minimize/eliminate unnecessary sun exposure during the study. If sun exposure is unavoidable, sunscreen with a sun protection factor (SPF) of minimum 30 should be utilized. Intentional tanning is prohibited throughout the study.

3.5.5.4 General Restrictions

- Following enrollment in the study, subjects should continue all non-pharmacological therapies, such as physical therapy, as indicated and deemed appropriate for his/her physical condition.
- Subjects should not donate blood or receive any blood or blood products within 4 weeks prior to Visit 1 and throughout the study duration.
- Routine household contact with children or others vaccinated with live vaccine components (e.g., varicella, or attenuated typhoid fever, oral polio, attenuated rotavirus or inhaled flu vaccines) should be avoided during the study and for 6 weeks after the last dose of study drug.
- Travel to countries with known high prevalence of tuberculosis should be avoided from the time of signing the informed consent through the Follow-up Visit.

3.5.6 Procedure Definitions

3.5.6.1 *Static Physician's Global Assessment (sPGA)*

The sPGA will be performed on psoriatic lesions overall by the Investigator according to the schedule summarized in [Table 1](#).

The sPGA is used to determine the severity of subject's psoriatic lesion at a given time point. Every effort should be made to perform the sPGA assessments by the same evaluator throughout the study. The psoriatic lesion will be graded for induration, erythema and scaling based on the scales below. The sum of the 3 scales will be divided by 3 to obtain the final sPGA score.

Induration (I)

- 0 = no evidence of plaque elevation
- 1 = barely palpable
- 2 = slight but definite elevation, indistinct edge
- 3 = elevated with distinct edges
- 4 = marked plaque elevation, hard/sharp borders

Erythema (E)

- 0 = no evidence of erythema (post inflammatory hyperpigmentation and/or hypopigmentation may be present)
- 1 = faint erythema
- 2 = light red coloration
- 3 = red coloration
- 4 = dusky to deep red coloration

Scaling (S)

- 0 = no evidence of scaling
- 1 = occasional fine scale
- 2 = fine scale predominates
- 3 = coarse scale predominates
- 4 = thick, coarse scale predominates

Add I+E+S = _____ /3 = _____ (Total Average)

Physician's Static Global Assessment based upon above Total Average

- 0 = Cleared, except for residual discoloration
- 1 = Minimal – majority of lesions have individual scores for I+E+S/3 that averages 1
- 2 = Mild – majority of lesions have individual scores for I+E+S/3 that averages 2
- 3 = Moderate – majority of lesions have individual scores for I+E+S/3 that averages 3
- 4 = Severe – majority of lesions have individual scores for I+E+S/3 that averages 4

Note: Scores should be rounded to the nearest whole number (e.g., if the total is ≤ 1.49 , the score should be 1; if the total is ≥ 1.50 , the score should be 2) except if the score is >0 and <1 , score should be treated as 1.

3.5.6.2 Psoriasis Body Surface Area (BSA) and Psoriasis Area and Severity Index (PASI)

The BSA assessment will be performed according to the schedule summarized in [Table 1](#).

The total BSA affected by plaque-type psoriasis will be estimated from the percentages of areas affected, including head, trunk, upper limbs and lower limbs (see below for PASI assessment). The following calculations will be done: each reported percentage will be multiplied by its respective body region corresponding factor (head = 0.1, trunk = 0.3, upper limbs = 0.2, lower limbs = 0.4). The resulting 4 values will be added up to estimate the total BSA affected by plaque-type psoriasis.

Psoriasis area and severity index (PASI), a quantitative rating score to assess the severity of psoriatic lesions based on the area coverage and plaque appearance will be performed according to the schedule summarized in [Table 1](#).

Every effort should be made to perform the BSA and PASI assessments by the same evaluator throughout the study.

The PASI score will be derived as indicated in [Table 8](#).

The head, trunk, upper limbs and lower limbs are assessed separately for erythema, thickening (plaque elevation, induration) and scaling (desquamation). The average degree of severity of each sign in each of the four body regions is assigned a score of 0 to 4. The area covered by lesions on each body region is estimated as a percentage of the total area of that particular body region. Listed below are further practical details to help with the assessment:

1. The neck is assessed as part of the head.
2. The axillae and groin are assessed as part of the trunk.
3. The buttocks are assessed as part of the lower limbs.
4. When scoring the severity of erythema, scales should not be removed.

Because the head and neck, upper limbs, trunk and lower limbs correspond to approximately 10%, 20%, 30% and 40% of the body surface area, respectively, the PASI score is calculated using the following formula:

$$\text{PASI} = 0.1(\text{EH}+\text{IH}+\text{DH})\text{AH} + 0.2(\text{EU}+\text{IU}+\text{DU})\text{AU} + 0.3(\text{ET}+\text{IT}+\text{DT})\text{AT} + 0.4(\text{EL}+\text{IL}+\text{DL})\text{AL}$$

The PASI scores can range from 0, corresponding to no signs of psoriasis, up to a theoretic maximum of 72.0, corresponding to maximal signs of psoriasis.

Table 8. The PASI Scoring

Body region	Erythema (E)	Thickening (plaque elevation, induration, I)	Scaling (desquamation, D)	Area score (based on true area %, A)*
Head (H) [†]	0=none 1=slight 2=moderate 3=severe 4=very severe	0=none 1=slight 2=moderate 3=severe 4=very severe	0=none 1=slight 2=moderate 3=severe 4=very severe	0 = 0% 1 = 1-9% 2 = 10-29% 3 = 30-49% 4 = 50-69% 5 = 70-89% 6 = 90-100%
Trunk (T) [‡]	0=none 1=slight 2=moderate 3=severe 4=very severe	0=none 1=slight 2=moderate 3=severe 4=very severe	0=none 1=slight 2=moderate 3=severe 4=very severe	0 = 0% 1 = 1-9% 2 = 10-29% 3 = 30-49% 4 = 50-69% 5 = 70-89% 6 = 90-100%
Upper limbs (U)	0=none 1=slight 2=moderate 3=severe 4=very severe	0=none 1=slight 2=moderate 3=severe 4=very severe	0=none 1=slight 2=moderate 3=severe 4=very severe	0 = 0% 1 = 1-9% 2 = 10-29% 3 = 30-49% 4 = 50-69% 5 = 70-89% 6 = 90-100%
Lower limbs (L) [§]	0=none 1=slight 2=moderate 3=severe 4=very severe	0=none 1=slight 2=moderate 3=severe 4=very severe	0=none 1=slight 2=moderate 3=severe 4=very severe	0 = 0% 1 = 1-9% 2 = 10-29% 3 = 30-49% 4 = 50-69% 5 = 70-89% 6 = 90-100%

* Percentage (not score) of body region (not whole body) affected will be entered in the CRF

† Neck is assessed as part of the Head (H) body region.

[figure not shown]
‡ Axillae and groin are assessed as part of the Trunk (T) body region.

§ Buttocks are assessed as part of the Lower limbs (L) body region.

3.5.6.3 *Skindex-16*

Subjects will complete Skindex-16 questionnaire according to the schedule summarized in [Table 1](#).

Skindex-16 is a 16-item, skin-related QOL questionnaire (see [Appendix 2](#)) and has 3 domain scores: symptoms, emotions, and functioning. Each 16-item QOL questionnaire will be reported on a scale of 0 to 6. Each raw score will be multiplied by 16.667, thus all responses will be transformed to a linear scale of 100 (i.e., from 0 [no effect] to 100 [effect experienced all the time]). If more than 25% of the responses missing, the scale is considered missing. An item with multiple answers is considered missing.

[figure not shown]

3.5.6.5 *Itch Numeric Rating Scale (NRS)*

The Itch NRS is a validated, self-reported instrument for measurement of itch intensity. It uses a 24-hour recall period and asks subjects to rate the worst itch intensity on an 11-point scale ranging from 0 (no itch) to 10 (worst itch imaginable).

The Itch NRS scores will be recorded by the subject using the e-diary once daily (before study drug administration once the subject is randomized) preferably at the same time of the day each

day from Screening through the last visit. Site will dispense the e-diary device at Screening Visit and train the subject on how to use the device.

3.5.6.7 Physical Examination

The physical examinations will be performed by a physician or a qualified designee according to the schedule summarized in [Table 1](#) and will include examination of the following body systems: general appearance, skin (including hair and nails), HEENT (head, ears, eyes, nose, throat), neck/thyroid, chest/lungs, cardiovascular, gastrointestinal, neurological, psychiatric/emotional, lymphatic and musculoskeletal systems.

3.5.6.8 Height and Weight Measurements and Body Mass Index Calculation

The height and weight measurements will be performed according to the schedule summarized in [Table 1](#). Subjects will remove their shoes and wear light clothing to be consistent between measurements of height and/or weight. The BMI will be calculated at Visit 1 using the following equation: (weight (kg)/[height (m)²]), where the weight in kilograms will be documented to one decimal place and the height in centimeters will be rounded to the nearest whole number.

3.5.6.9 Medical History

A complete medical history will be performed at Visit 1 and will include evaluations for past or present conditions.

Any pre-existing conditions detected at Visit 1 (e.g., abnormalities in ECG, physical examination, vital signs and laboratory tests) are considered medical history.

3.5.6.10 Prior and Concomitant Medications

Information pertaining to all medications use (including prescription, over-the-counter, supplements, vitamins and minerals) will be collected for the period of at least 30 days prior to Visit 1 and throughout the study.

Information regarding any prior/current psoriasis therapies and/or immunomodulating therapies, as listed in Section [3.5.5.1.1](#) will be collected according to the schedule summarized in [Table 1](#).

3.5.6.11 Vital Signs

Vital sign assessments including blood pressure, heart rate, respiratory rate and body temperature (°C) will be performed in sitting position according to the schedule summarized in [Table 1](#). Subjects must rest in a sitting position for at least 5 minutes in preparation for blood pressure and heart rate assessments.

3.5.6.12 12-Lead ECG

12-lead ECG recordings and conduction intervals including RR, PR, QRS, QT and Fridericia-corrected QT interval (QT_cF) will be obtained according to the schedule summarized in [Table 1](#). The Investigator or designee will review and assess each individual ECG report and the interpretation of the actual findings, rather than the automatic printout, results on the ECG tracing will be documented. Subjects will lay supine without pillows for at least 5 minutes prior to the 12-lead ECG assessment.

3.5.6.13 Hematology

Blood samples to assess complete blood count including erythrocytes, hematocrit, hemoglobin, platelets, leucocytes and differential (percent and absolute [neutrophil, eosinophil, basophil, lymphocyte, monocyte]) will be obtained under fasted conditions according to the schedule summarized in [Table 1](#).

3.5.6.14 Serum Biochemistry

Blood samples to assess ALP, albumin, ALT, AST, bilirubin, blood urea nitrogen, calcium, carbon dioxide, chloride, creatinine phosphokinase, creatinine, gamma-glutamyl transferase, globulin, glucose, C-reactive protein, lactate dehydrogenase, low-density lipoprotein cholesterol, phosphate, potassium, protein, sodium, total cholesterol, triglyceride, urate will be obtained under fasted conditions according to the schedule summarized in [Table 1](#).

3.5.6.15 Coagulation

Blood samples to assess thromboplastin time (PT) and activated partial thromboplastin time (aPTT) will be obtained as measures of blood coagulation according to the schedule summarized in [Table 1](#). International normalized ratio will also be calculated.

3.5.6.16 Viral Serology

Blood samples to assess HBc antibodies, HBsAg, HCV antibodies and HIV antibodies will be obtained at Visit 1.

3.5.6.17 Drugs of Abuse and Alcohol Screen

Urine samples to assess amphetamines, barbiturates, benzodiazepines, cannabinoids, cocaine metabolites, opiates, ethanol, methadone, methylenedioxymethamphetamine and oxycodone will be obtained at Visit 1.

3.5.6.18 Urinalysis

Urine samples to assess bilirubin, occult blood, color, glucose, ketone, leukocyte esterase, nitrite, pH, protein, specific gravity, turbidity and urobilinogen, as well as for a microscopic exam (to be performed only if the macroscopic exam is abnormal), including bacteria, cast, crystals, epithelial cells, mucus threads, erythrocytes, leukocytes and budding yeast will be obtained under fasted conditions according to the schedule summarized in [Table 1](#).

3.5.6.19 Glycosylated Hemoglobin

Blood samples to measure glycosylated hemoglobin (HbA1c) will be obtained at Visit 1.

3.5.6.20 *Pregnancy Test*

Blood samples from all female subjects will be collected at Visit 1 for a serum pregnancy test to assess human chorionic gonadotropin (β HCG) levels. At Visits 2 through 8, urine pregnancy tests will be performed only for female subjects of childbearing potential.

3.5.6.21 *Follicle-stimulating Hormone*

Blood samples to assess the menopausal status will be collected at Visit 1 only from female subjects who report a history of or lack of menses but onset within 12 months with no other identified biological/surgical cause.

3.5.6.22 *QuantiFERON®-TB Gold Plus Test*

[figure not shown]
The QuantiFERON®-TB Gold Plus test (according to the local standard of care) may be used as tuberculosis screening tools for the study during the Screening Period. Blood samples will be collected, processed and shipped during the Screening Period, according to the laboratory instructions. In case of an indeterminate QuantiFERON®-TB Gold Plus test, the test may be repeated one time if results can be obtained in time prior to Visit 2. If the retest is also indeterminate, subject will not be eligible for the study.

[figure not shown]
Subjects with positive QuantiFERON®-TB Gold Plus test and a history of treated latent TB who have documented evidence of completed adequate treatment at least 12 months prior to Visit 2 may participate in the study, if all other study restrictions required by the protocol are met.

Subjects who have had household contact with a person with active tuberculosis are excluded, unless appropriate and documented prophylactic treatment for TB, as recommended by local guidelines, was completed at least 30 days prior to Visit 2.

3.5.6.23 *Chest Radiography*

Chest radiography to include two views (anterior-posterior and lateral) will be obtained during the Screening Period in all subjects. If adequate chest radiography has been performed within 3 months (12 weeks) prior to Visit 1 and documentation (including interpretation of TB status) is available, it will be provided to the Investigator for review and documented in the subject's record. This radiography may be utilized to determine eligibility of the subject. To be considered eligible for the study, the radiography must be negative for active tuberculosis infection; however, the Investigator may decide to exclude the subjects based on clinically-significant chest radiography findings other than tuberculosis (e.g., due to an acute or chronic inflammatory process), according to his/her judgment.

3.5.6.25 *Photography*

If collecting photographs is raised as the reason for not participating in the study, the subject still can be part of the study without collecting photographs. Subjects who do not raise this objection will be required to take photographs of four half-body views (i.e., upper anterior, lower anterior, upper posterior and lower posterior)

according to the schedule presented in [Table 1](#). In all collected photographs, subject identification (e.g., eye, mouth, tattoos) will be blinded. Please refer to the photography manual for detailed instructions regarding collection, processing, storage and transmission of photographs.

3.5.6.26 *Blood Samples for Pharmacokinetic Assessments*

Blood samples for quantification of JTE-451 in plasma will be obtained according to the schedule summarized in [Table 1](#) and [Figure 2](#).

[figure not shown]
At each study visit during the treatment period (i.e., Visit 2 through Visit 7 [except for Visit 3, when no PK sample collection will be performed]), the actual dose time, as well as the sample collection time will be documented for PK data analysis. Refer to the laboratory manual for specific instructions regarding collection and processing of blood samples for PK assessments.

3.5.6.27 *Analysis of JTE-451 in Plasma*

JTE-451 will be analyzed in plasma using a validated high performance liquid chromatography/tandem mass spectrometry (HPLC-MS/MS) method.

The laboratory performing the JTE-451 assessments will be unblinded to facilitate analysis of only the samples from JTE-451-administered subjects. Plasma samples from placebo subjects may be analyzed as needed.

3.5.7 Clinical Institutions and Laboratories

3.6 Adverse Events

3.6.1 Safety Definitions

Akros complies with the following International Council for Harmonization of Technical Requirements for Pharmaceuticals for Human Use (ICH) AE definitions:

Adverse Event: An AE is any untoward medical occurrence in a patient or clinical investigation subject administered a pharmaceutical product and which does not necessarily have a causal relationship with this treatment. An AE can therefore be any unfavorable and unintended sign (including an abnormal laboratory finding), symptom, or disease temporally associated with the use of a medical (investigational) product, whether or not related to the medical (investigational) product.

Serious Adverse Event (SAE): An SAE is defined as any untoward medical occurrence at any dose that meets any of the following criteria:

- results in death
- is life-threatening
- requires inpatient hospitalization or prolongation of existing hospitalization
- results in persistent or significant disability or incapacity
- is a congenital anomaly or birth defect
- other important medical event

Note: Important medical events that may not immediately result in death, be life-threatening, or require hospitalization but may be considered SAEs when, based upon appropriate medical judgment, they may jeopardize the patient or subject or may require medical or surgical intervention to prevent one of the outcomes listed in this definition above. Examples of such important medical events include allergic bronchospasm requiring intensive treatment in an emergency room or at home, blood dyscrasias or convulsions that do not result in hospitalization, or the development of drug dependency or drug abuse.

Adverse Drug Reaction: All noxious and unintended responses to an investigational medicinal product (IMP)-related to any dose administered.

Note: The phrase "responses to a medicinal product" means that a causal relationship between the medicinal product and an adverse event is at least a reasonable possibility, i.e., the relationship cannot be ruled out.

Unexpected Adverse Drug Reaction: An adverse drug reaction, the nature (specificity) or severity of which is not consistent with the applicable product information (e.g., IB).

Death: Death represents an outcome, not an event term. The medical condition with the fatal outcome should be reported unless the cause of death is unknown, in which case the term "Death" is acceptable.

Inpatient Hospitalization/Prolongation of Hospitalization: Any admission (even if less than 24 hours) to a healthcare facility. Admission also includes transfer within the hospital to an acute/intensive care unit (e.g., medical floor to the coronary care unit). Initial and prolonged hospitalizations that **do not** meet this SAE criterion include those due to social and/or convenience reasons (e.g., lack of personal care at home, unable to transfer to non-acute facility), admission to rehabilitation/hospice/skilled nursing facilities, emergency room visits,

same-day/outpatient/ambulatory procedures, and those for pre-planned, elective procedures for a pre-existing condition that did not worsen after the informed consent has been signed (no AE present). However, if the hospitalization was prolonged due to a complication of a pre-existing condition, the complication (same diagnosis) would qualify as an SAE.

Disability: A substantial disruption of a person's ability to conduct normal life functions.

Life-threatening: Any AE that places the patient or subject, in the view of the Investigator, at immediate risk of death, i.e., it does not include an event that had it occurred in a more severe form, might have caused death.

Physical Examination, Vital Signs, Laboratory Test and ECG Abnormalities: Any abnormalities fulfilling the criteria for an SAE should be reported as such, in addition to being recorded as an AE in the CRF. Any abnormal vital sign, physical finding or laboratory/ECG result which is clinically-significant (i.e., meets one or more of the following conditions) should be recorded as a single diagnosis on the AE page in the CRF:

- Accompanied by clinical symptoms
- Leads to permanent discontinuation of study drug
- Requires a change in concomitant therapy (e.g., addition of, interruption of, discontinuation of, or any other change in a concomitant medication, therapy or treatment).

This does not apply to abnormal vital signs, physical finding or laboratory/ECG results that do not meet the clinical-significance criteria or parameters that are a result of an AE, which has already been reported.

Pre-existing conditions detected at the Screening Visit (Visit 1), including abnormalities in ECG, physical examination, vital signs and laboratory tests, are considered to be medical history.

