3.4 Removal of Subjects from the Study

A subject will not participate further in the study under the following conditions:

1. Death
2. Adverse Event: a clinical or biological adverse event or intercurrent condition(s), requiring study drug discontinuation, whether or not related to the study drug.

If grade 3 findings (defined as severe or medically significant but not immediately life-threatening; hospitalization or prolongation of hospitalization indicated; disabling; limiting self-care activities of daily living such as bathing, dressing, undressing, feeding self, using the toilet, taking medication, but not bedridden), according to the common terminology criteria for adverse events (CTCAE)¹⁴, are noted in a subject, he/she must be promptly evaluated by the Investigator (e.g., repeat tests, evaluation of the baseline parameters, concomitant medications) for potential withdrawal from the study. Every effort should be made to discuss this with the Medical Monitor prior to final decision, unless not feasible, based on safety considerations.

3. Withdrawal by Subject: subjects have the right to withdraw from the study at any time. However, if a subject withdraws consent because of experiencing an adverse event, the reason for subject termination should be documented as an adverse event.
4. Non-compliance with Study Drug (i.e., <80% or >120% compliance at two consecutive study visits; exceptions on a case-by-case basis may be permitted if approved by Sponsor or designee).

Note: Compliance will be evaluated at every study visit during the Treatment Period. If compliance of <80% or >120% is identified at a study visit, the Investigator or designee should counsel the subject and ensure steps are taken to improve compliance.

5. Inclusion/Exclusion Criteria Not Met: If a subject who did not meet one or more of the study inclusion or exclusion criteria is identified after randomization, the Investigator, Medical Monitor and Sponsor will review that subject profile, including the medical history, prior and concomitant medications, physical examination, vital signs, 12-lead ECGs and clinical laboratory test results. An exception may be permitted on a case-by-case basis if the subject was randomized into the study due to a minor error determined to be of no clinical and/or safety risk to the subject.

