- Possibly Related: The AE follows a reasonable temporal sequence from the administration of the study drug and follows a known or plausible response pattern to the study drug, but could readily have been produced by a number of other factors.
- Related: The AE follows a reasonable temporal sequence from the administration of the study drug; follows a known or expected response pattern to the study drug; is confirmed by improvement on stopping or reducing the dosage of the study drug (de-challenge) and reappearance of the event on repeat exposure (re-challenge); and cannot be reasonably explained by the participant's clinical state.

Action Taken with Regard to Study Drug:

The evaluation of the action taken with the study drug will be assessed using the following four definitions:

- Dose Not Changed: The subject was on treatment with the study drug when the AE occurred, and the study drug dosing was maintained at the same dose level
- Drug Interrupted: The subject was on treatment with the study drug when the AE occurred, and the study drug dosing was temporarily discontinued and then re-started
- Drug Withdrawn: The subject was on treatment with the study drug when the AE occurred, and the study drug dosing was permanently discontinued
- Not Applicable: The subject was not receiving treatment with the study drug when the AE occurred (i.e., AE occurred before the first study drug administration or after the last study drug administration), or if the subject died.

Other Action Taken:

- None
- Additional Treatment Given for the AE
- Therapeutic/ Diagnostic Procedure
- Other (including discontinuation/reduction of a concomitant medication due to the AE)

Outcome to Date:

- Not Recovered/Not Resolved: The subject has not yet recovered from the AE; the event has not improved (follow-up of all serious AEs will be continued until the overall clinical outcome has been ascertained).
- Recovering/Resolving: The subject has not yet recovered from the AE, however, the event is improving (follow-up of all serious AEs will be continued until the overall clinical outcome has been ascertained).
- Recovered/Resolved: The subject recovered from the AE with no sequelae.
- Recovered/Resolved with Sequelae: The subject recovered from the AE with sequelae.
- Fatal: The subject's death was a result of the AE.

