5.3.7 Vital Signs

Vital signs and body weight are collected as scheduled in Table 1. Vital signs include systolic/diastolic blood pressure, heart rate, respiratory rate and body temperature (°C). Subjects must rest in a sitting position for at least 5 minutes in preparation for blood pressure and heart rate assessments. The following information will be derived for all vital signs and body weight:

- Change from baseline at all post-baseline visits
- Treatment-emergent PCS abnormalities, if applicable

5.3.8 12-Lead ECG

Twelve-lead ECG recordings and conduction intervals including RR, PR, QRS, QT and Fridericia-corrected QT interval (QTcF) are obtained according to the schedules summarized in **Table 1**. The QTcF (Fridericia's formula, QTcF = QT/RR^{1/3}) will be derived and reported in the database.

The following information will be calculated for each of the 12-lead ECG measurements:

- Change from baseline to all post-baseline visits
- Treatment-emergent PCS abnormalities, if applicable

The overall clinical interpretation of an ECG is assessed as follows: normal, abnormal not clinically significant or abnormal clinically significant.

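### Protocol 3.6.1 does not require an AE record for a non-serious, asymptomatic abnormality that only interrupts study drug, so such events can be absent from the TEAE and ADR tables

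*Protocol*

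**What the plan says.** Protocol 3.6.1, in the paragraph on abnormal physical findings, vital signs, laboratory tests and ECGs, defines clinical significance by a closed list. At least one of three conditions must be met:

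- first, the subject has symptoms along with the abnormal finding;
- second, the finding "Leads to permanent discontinuation of study drug";
- third, because of the finding, some other medicine or treatment has to be started, interrupted, stopped or otherwise altered.

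The word interruption occurs only in the third condition, where it refers to concomitant therapy and not to study drug. The paragraph then limits the instruction: "This does not apply to abnormal vital signs, physical finding or laboratory/ECG results that do not meet the clinical-significance criteria". A separate sentence at its start covers serious cases: "Any abnormalities fulfilling the criteria for an SAE should be reported as such, in addition to being recorded as an AE in the CRF".

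Three other places bear on the point. The general AE definition in the same section expressly includes an abnormal laboratory finding and sets no significance filter. Protocol 3.6.2 provides an action category, Drug Interrupted, in which "the study drug dosing was temporarily discontinued and then re-started". SAP 6.5.1 defines an ADR as a TEAE that is related, possibly related or of missing relationship to study drug.

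**The concern.** Safety and tolerability is a secondary objective, and the AE and ADR tables are where investigator judgement on severity and causality is summarized. An asymptomatic abnormality that makes an investigator pause dosing is informative about tolerability. If the value recovers off drug and dosing resumes, the episode is also the kind of evidence that the causality scale in Protocol 3.6.2 uses: its Related category refers to improvement on de-challenge and reappearance on re-challenge. Yet the recording rule counts a permanent stop and does not count a pause.

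For such an event the AE form need not be completed, so severity, causality, action taken and outcome need not be recorded there. They are hard to reconstruct reliably later.

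**Working it through.** No figure is stated in the plan and no formula applies. The check traces a finding from Protocol 3.6.1 to the AE page and on to the SAP tables.

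**Step 1: is the finding recorded as an AE?** In every case below the abnormality is asymptomatic and study drug is stopped because of it.

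| Case | Dosing | Other facts | Route under Protocol 3.6.1 | AE record required? |
|---|---|---|---|---|
| A | paused, restarted | no change in concomitant therapy, no SAE criterion met | none | No |
| B | paused, restarted | concomitant therapy changed | third condition | Yes |
| C | paused, restarted | an SAE criterion is met | SAE sentence | Yes |
| D | stopped permanently | otherwise as A | second condition | Yes |

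Only case A falls through. It differs from case D only in that dosing was restarted.

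**Step 2: what follows in the SAP?** A TEAE is by definition an AE (SAP 5.3.3) and an ADR is a subset of TEAEs (SAP 6.5.1). A case A finding that is not entered as an AE therefore cannot reach either set of tables.

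**Step 3: does another rule bring case A back in?**

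- Protocol 3.4 says that when CTCAE grade 3 findings "are noted in a subject, he/she must be promptly evaluated by the Investigator", but the evaluation is for potential withdrawal. It gives no instruction to record an AE.
- CTCAE grading in Protocol 3.6.2, including the SAE assessment for Grade 4 or 5, applies to something already called an AE.
- SAP 5.3.8 has each ECG classed as "normal, abnormal not clinically significant or abnormal clinically significant". That classification is not one of the three conditions in 3.6.1.

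**Step 4: where does the value still appear?**

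- Listings: all safety data are listed and PCS values flagged (SAP 6.5). Listings cover all collected data, including unscheduled visits (SAP 6 and 7).
- Liver table: an ALT of 8 x ULN meets the 3 x and 5 x limits in SAP Table 3.
- PCS table: neutrophils of 0.8 E3/mm3 meet the limit of 1.0 or below in SAP 10.1.
- ECG: the overall interpretation is summarized by time point and treatment group (SAP 6.5.6).
- Gaps: Protocol 3.5.6.14 measures phosphokinase (printed with creatinine) and LDL cholesterol. SAP 10.1 lists only the CPK MB fraction, with no limit, and gives no limit for LDL. An abnormality in these would be visible only in listings and descriptive statistics.

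None of these displays is specified to carry investigator causality or action taken with study drug.

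**The case against.** The strongest case on the other side has five parts.

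1. **The reach is narrow.** A reader might infer that any severe asymptomatic abnormality that pauses dosing is kept out of the AE tables. The text does not support that. SAE-qualifying abnormalities are recorded, and important medical events can qualify by medical judgement; the protocol names blood dyscrasias as an example, so low neutrophils might enter that way. A change in concomitant therapy is a further route. This stands and confines the point to case A.
2. **Recording is not forbidden.** Saying that the instruction does not apply removes a requirement; it does not impose a ban. The general AE definition still allows an investigator to record the finding. This stands: the most that can be said is that the finding need not be recorded.
3. **The values are reported elsewhere.** A reader might infer that these events survive only as table counts. Step 4 shows otherwise, since subject-level listings would show the abnormal value and any measured recovery. This stands for the values, but not for causality and action taken.
4. **Drug Interrupted is not contradicted.** That category serves every AE, including symptomatic ones, and its existence does not mean that every interruption defines an AE. This is fair. The mismatch is a poor fit, not a logical contradiction.
5. **A severity criterion is a policy choice.** A reader might conclude from Protocol 3.4 that every CTCAE grade 3 or higher value should be an AE. That section concerns evaluation for withdrawal, and reasonable statisticians differ on automatic AE reporting by grade. The documents do not require it.

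**Conclusion.** The point holds in a limited form. Under Protocol 3.6.1, a non-serious, asymptomatic laboratory, ECG, vital-sign or physical-examination abnormality that leads only to temporary interruption of study drug, without a change in concomitant therapy, need not be recorded as an AE. It can then be absent from the TEAE and ADR tables and lack causality, action taken and outcome. The list fits poorly with the general AE definition in the same section and with the Drug Interrupted category in 3.6.2.

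The size cannot be estimated. About 100 subjects are planned on JTE-451 (2 groups of about 50), but neither document gives a rate for such events, and any assumed rate would have to exclude cases already recorded through the SAE or concomitant-therapy routes. The number affected is unknown and could be zero. The conclusion rests on reading the three conditions as a closed list, which is how the protocol words them, and on investigators not recording more than the rule asks. It is a cheap improvement to safety recording and does not show that safety signals would be lost.

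**What to change.** In Protocol 3.6.1, widen the second condition so that temporary interruption of study drug counts alongside permanent discontinuation. Carry the same wording into the CRF completion guidance. In the same edit, reconcile the paragraph with the general AE definition earlier in 3.6.1 and with the action categories in 3.6.2, so that it is clear when an abnormal finding is an AE.

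This changes only what is written down once an investigator has interrupted dosing. It does not say when dosing should be interrupted, resumed or stopped. No CTCAE grade criterion is needed to close the gap.

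The cost is a short wording change, no extra tests or visits, and a few more AE entries. The added records would feed the existing TEAE tables by severity and causality and, where applicable, the ADR tables. SAP 6.5.1 names no table by drug interruption, so action taken would be read from the AE listing unless the separate mock tables provide one.
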